Approximately 270 children, age 3 months to ≤ 11 years, and their primary caregiver as participants, for a total of 540 participants (270 pairs), will be randomized in 1:1 ratio to either Crisaborole (2% BID) or vehicle treatment and will be followed for 2 weeks, with an objective of approximately 50% of recruited child participants being ages 5 years old or younger. For this study, we will employ a simple randomization procedure. Participants will be randomly assigned (1:1) using computerized random numbers to receive either crisaborole or the vehicle. The participants will be asked to apply a thin even-layer of Crisaborole 2% or vehicle twice daily (excluding mouth, eyes, and vagina, per label), to all locations with active lesions and record location and time of application on the daily dosing form (as identified on the Dosing Record Sheet, breastfeeding women will be instructed to use the provided gloves when applying crisabrole/vehicle). The study will be comprised of an initial screening/baseline visit for children participants who have an existing diagnosis of symptomatic AD, screened and enrolled in the study along with their primary caregivers after signing an informed consent (or parents/guardians and assent when appropriate). Upon enrollment child participants and caregiver participants will complete a one week acclimation and training phase, where the children will not be on medication, for wearing accelerometry/actigraphy and performing observer-reported outcome assessments (caregivers for participants) and self-reported outcome assessments (caregivers). After the one week acclimation and training phase, the child participants will be on a Crisaborole or vehicle treatment for two consecutive weeks. During those 2 weeks, the children, 3 months up to <2 years will wear one actigraphy or one accelerometry device on each wrist and one actigraphy or one accelerometry device on each ankle (optional for those who have active AD on location of device placement, with a minimum of at least one wrist device needed for enrollment). Children 2 years to ≤ 11 years will wear one actigraphy or one accelerometry device on each wrist (optional for those who have active AD on location of device placement, with a minimum of at least one wrist device needed for enrollment). The primary caregiver (parents/guardians) will also wear one accelerometer device on each wrist and complete daily assessments related to scratching, sleeping habits, pain, AD severity, quality of life, and device comfort questionnaires (parent/guardian will complete as appropriate). The participants will be asked to return to the laboratory

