8.4 Research Related Injury

Possible social risks: These are extremely low in this study and pertain to the unintentional release of personal information.

Mitigation of social risks: To safeguard confidentiality and the privacy of protected information, each study participant will be assigned a unique code number. A separate file linking the participants' name with study number and identifiers will be kept in a password-protected data file, accessible only by the PI and the study coordinator. All study forms will be kept in secure locked file cabinets. The study investigators will assume full responsibility to maintain the confidentiality of all data. All study results will be presented only as statistical aggregates that will neither identify, nor permit identification of, individual participants.

Possible risk associated with digital health devices: The risks associated with these devices include physical discomfort if the participant is not used to wearing wrist accelerometers and/or ankle devices, and possible skin irritation or reaction, such as an AD flare-up in children with the skin condition. If the participant experiences skin irritation or notice signs of an AD flare-up in the area that the child wears the device(s), they will be instructed to remove the device(s) and notify the study team immediately.

Mitigation of risks associated with digital health devices: If the participant is unable to wear the device due to discomfort (or AD flare up) the participant will notify study staff and the Principal Investigator may allow the participant to continue the study without wearing the discomforting device or withdraw the

participant from the study. Devices will be optional for child participants who have active AD on location of device placement, with a minimum of at least one wrist device needed for enrollment.

Possible risk associated with tape stripping: Tape stripping is routinely performed and is considered a minimally invasive approach for identifying biomarkers for Atopic Dermatitis and is an acceptable alternative to traditional biopsies. The only minimal risk associated with tape stripping is mild discomfort and potentially superficial surface reddening of the skin at the location of the tape. This is typically reported after 50-60 tape stripplings. In this study we will only be doing ~20 tape stripplings per sample. Tape stripping sensation is similar to removal of a band-aid.

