The primary and secondary endpoints will be tested at the significance level of 0.05 (2-sided). There is no multiplicity adjustment. Number, percent and 95% confidence interval (CI) will be presented for binary endpoints. Descriptive summary statistics (n, Mean, Std. Dev, Median, Min., Max.) will be presented for continuous endpoints. In addition, graphics may be used to present the data.

The primary objective is to evaluate the effects of Crisaborole on itch and night-time scratch. The primary endpoints include number of scratching episodes (children aged 2 – \leq 11 years), duration of scratching (children aged 2 – \leq 11 years), and ORIA (ages 3 months to \leq 11 years). For these endpoints, change from baseline will be analyzed using a mixed-effects model with repeated measures (MMRM) including data from Day 1 (for accelerometry measured scratch episodes and duration)/Day 2 (for ORIA) to Day 15 with baseline score as a covariate and an unstructured covariance matrix. The least-squares (LS) means and

the corresponding 95% CIs, the LS mean difference between treatment groups, and the corresponding 95% CI will be presented for change from baseline for all postbaseline timepoints. As a sensitivity analysis, instead of daily data, average of every 3 days data will be used to account for day-to-day variation.

The binary endpoints will be descriptively summarized using sample size, number, percentage and 95% confidence interval (CI) of percentage at each time point. Binary data will be analyzed by comparing response rates between treatment groups. Normal approximation to the difference in response rates will be used to obtain p-values and 95% CI. For binary endpoints analyzed at each scheduled visit separately, participants who drop out for any reason or require a prohibited medication for the treatment of their atopic dermatitis will be defined as “non-responsive” at all subsequent visits. This method of handling missing response is known as missing response as non-response (MR-NR).

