Mixed model repeated measures (MMRM) will be used to analyze longitudinal continuous data. Treatment, visit, treatment-by-visit interaction are fixed effects in the model, baseline value as a covariate. Within-participant variability will be accounted for using a random effect with the unstructured covariance matrix. If this is a convergence issue, other type of covariance matrix will be used. The following structures will be executed in the order specified (essentially in decreasing order of complexity) until convergence is achieved: heterogeneous Toeplitz, heterogeneous first order autoregressive, autoregressive, heterogeneous compound symmetry, compound symmetry, and variance components. The first structure yielding convergence will be used as the primary analysis. The Kenward and Roger method for calculating the denominator degrees of freedom for tests of fixed effects will be used. Least square (LS) estimates of mean values and the LS mean differences between crisaborole 2% BID and vehicle groups at each visit will be derived from the model. The corresponding p-value, standard error (SE) and 95% CI will also be derived from the model.

ANCOVA model will be used to analyze nonlongitudinal continuous endpoints with treatment as a factor baseline value as a covariate. Least square (LS) estimates of mean values and the LS mean differences between crisaborole 2% BID and vehicle groups at each visit will be derived from the model. The corresponding p-value, standard error (SE) and 95% CI will also be derived from the model.

For any accelerometry/actigraphy continuous variables that exhibit right skewed distribution (i.e. skewed to positive values), log transformation may be used as appropriate. Specifically, for number of scratching, length of time scratching, arousals from sleep, WASO, and sleep onset latency, $\log(x+1)$ transformation will be employed (to include possible zero values). For time duration between scratching, $\log(x)$ will be employed.

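### Does the lack of a written rule for nights with only one wrist device put the two scratch primary endpoints at risk?

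*Combined protocol and SAP*

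**What the plan says.** Section 3 sets the planned wear: "Children 2 years to ≤ 11 years will wear one actigraphy or one accelerometry device on each wrist". Devices are optional where there is active disease at the site, "with a minimum of at least one wrist device needed for enrollment". That minimum is a condition of entry and does not define a scorable night.

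Section 8.4 foresees removal during the study for irritation or a local flare: if families "notice signs of an AD flare-up in the area that the child wears the device(s), they will be instructed to remove the device(s", and "the Principal Investigator may allow the participant to continue the study without wearing the discomforting device"; withdrawal is the stated alternative.

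In Section 9, "The primary endpoints include number of scratching episodes" and duration of scratching, both for ages 2 to 11, together with ORIA from 3 months. For these, "change from baseline will be analyzed using a mixed-effects model with repeated measures (MMRM) including data from Day 1" (Day 2 for ORIA) to Day 15, with the baseline score as covariate. A log(x+1) transformation is specified "for number of scratching, length of time scratching, arousals from sleep, WASO, and sleep onset latency". Missing longitudinal values are left to the mixed model under missing at random. The one sensitivity analysis given for these endpoints uses three-day averages.

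Section 2 lists non-wear time as a device output. Section 10.2 sends the watch data to the sponsor for processing, with results shared back to the university, and records serial numbers and file metadata.

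**The concern.** A child can have a two-wrist baseline and then one-wrist nights on treatment, by a route the protocol itself provides. Such a night still yields a number, so the missing-data rule does not plainly cover it. Read literally, it counts as observed and is set against a two-wrist baseline. Part of the resulting change would then reflect the lost device and not the child's scratching.

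Removal is triggered by skin reactions at the wrist, which treatment could affect. If one arm removed more devices, two of the three primary endpoints could shift. Each is tested at two-sided 0.05 without multiplicity adjustment. The size and even the direction of the shift would depend on a rule that Section 9 does not state.

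**Working it through.** **1. The plan's own figure.** The sample size rests on the itch score: difference 1.0, SD 2.6, two-sided 5%, 85% power (Section 9). Per arm, n = 2 × (1.960 + 1.036)² × 2.6² / 1.0² = 121.4, rounded up to 122, or 244 in total. This matches the plan, and power at 122 per arm is 85.2%. Allowing for about 10% dropout gives 244/0.9 = 271 or 244 × 1.1 = 268; the plan's 270 lies between. No figure is given for the scratch endpoints, so there is no power statement for this concern to upset.

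**2. One night in one child.** Let s be the share of recorded scratching on the wrist that loses its device (assumed; not in the documents). If true scratching is unchanged, the one-device night relative to a two-wrist baseline is:

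| s | wrists summed: 1−s | wrists averaged: 2(1−s) | higher wrist: (1−s)/max(s, 1−s) |
|---|---|---|---|
| 0.2 | 0.80 | 1.60 | 1.00 |
| 0.5 | 0.50 | 1.00 | 1.00 |
| 0.8 | 0.20 | 0.40 | 0.25 |

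None of these three rules is neutral for every s, and averaging always gives twice the summed factor.

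**3. How many children.** Section 3 has a target, "with an objective of approximately 50% of recruited child participants being ages 5 years old or younger". Of 270 children, about 270 × 0.5 = 135 are therefore older than 5. The 2 to 11 group lies between 135 (if every younger child is under 2) and 270, or about 68 to 135 per arm before dropout.

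**4. Effect on the arm comparison.** Suppose k more vehicle than crisaborole children are on one device on a given night, with n per arm and no true effect. The crisaborole/vehicle ratio is multiplied by exp(−(k/n) × d), where d is the shift in log(x+1). Take an assumed 20 episodes on a two-wrist night:

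- Summed: d = ln(17/21) = −0.211 (s = 0.2), ln(11/21) = −0.647 (s = 0.5), ln(5/21) = −1.435 (s = 0.8).
- Averaged: d = ln(17/11) = +0.435, 0, and ln(5/11) = −0.788.
- Higher wrist: d = 0, 0, and ln(5/17) = −1.224.

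With k = 10 and n = 68, k/n = 0.147:

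| s | summed | averaged | higher wrist |
|---|---|---|---|
| 0.2 | 1.03 | 0.94 | 1.00 |
| 0.5 | 1.10 | 1.00 | 1.00 |
| 0.8 | 1.24 | 1.12 | 1.20 |

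With k = 10 and n = 135, the summed factors at s = 0.2 and 0.5 are 1.02 and 1.05, and the averaged factor at s = 0.2 is 0.97. With k = 5 and n = 135 they are 1.01, 1.02 and 0.98. A simulation with assumed log SD 0.8, baseline correlation 0.6 and median 20 agreed for s = 0.2 and 0.5 (for example 1.098 against 1.10). With k = 0 and the same s in both arms, every factor is 1.00.

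**5. What the documents supply for k and s.** Nothing. The local reactions that Section 8.4 lists for crisaborole and for vehicle are largely the same, so the text gives no ground for expecting k in either direction.

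**6. Who applies the rule.** Section 9 has both the laboratory and the sponsor running statistical analyses. Section 10.2 describes the step from raw watch data to results once, at the sponsor, and the laboratory receives the output. Nothing says that the laboratory derives nights separately.

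**The case for a change.** The strongest case for a change is this. The protocol creates the situation and the analysis section is silent on it. Missing at random does not answer it, because a one-wrist night is a value. The study is single blind, and the text supplied does not say who is blinded, so a rule chosen late could be influenced by results. Section 9 also wants variability estimates for future studies and a comparison of device measures with reported outcomes. Both use the same derived quantity, whether or not removal differs by arm.

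The silence stands, and it is wider than one-device nights. No wrist-combination rule or valid-night definition is written for any night, and the nights that form the scratch baseline are not named. Randomisation and device issue both fall at V01 (Day -7), so a device could come off during the unmedicated acclimation week, inside a possible baseline period. Section 3 describes one device per wrist, while the Schedule of Activities and the V01 list carry two wrist entries for ages 2 to 11. Extra noise in the variability estimates is possible, but its size is unknown.

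The step from silence to a wrong result does not stand. Two groups scoring the same nights differently is not what Section 10.2 describes. The larger factors above need the smallest possible group, an imbalance of 10/68, or about 15 percentage points, on one night, and a removed wrist that carried half or more of the scratching. Single-wrist measurement is also not foreign to this design: the endpoint definition and exclusion criterion 13 both accept a child with one wrist device throughout.

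**Conclusion.** The concern does not call for a change to the plan. What is missing is derivation detail of the kind a device-processing specification supplies. The sponsor cannot produce nightly values without settling it. Non-wear time and device metadata are collected, so the number of devices behind each night can be recovered and the choice examined.

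Following the plan is not shown to give a wrong answer. Between-arm bias requires unequal removal together with a derivation that depends on device count. Under the assumptions shown (20 episodes, 10 extra vehicle children of 68 per arm, s from 0.2 to 0.8) the factor runs from 0.94 to 1.24, and it is 1.00 when removal and s are equal across arms. The documents do not favour any value in that range, so neither sign nor size can be claimed.

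An added sensitivity analysis would not settle the matter either. Leaving these nights out relies on the same missing-at-random assumption that the plan already makes, although removal follows a local flare. Endpoints, model, ORIA and sample size are unaffected.

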9. DATA ANALYSIS

Study Hypotheses: The primary objective of this study is to evaluate the reduction of itch and nighttime scratch (as measured by accelerometry/actigraphy and Observer Reported Itch Assessment (ages 3 months to \leq 11 years old) with application of crisaborole. A clinically significant change in scratching as measured by accelerometry/actigraphy has not yet been determined. The relationship between accelerometry/actigraphy scratching parameters and PRO scratching assessments is being studied currently. This study adds to the knowledge base by studying the association between changes in PRO scratching assessments and changes in accelerometry/actigraphy scratching parameters when treatment is initiated or changed. Estimates of their variability from this study can also fill the literature gap and be used to help design future studies.

As this study is a research collaborative agreement, both the Laboratory for Human Neurobiology and the collaborator/sponsor will perform statistical analyses. Only deidentified data is shared with the collaborator.

Sample Size: The sample size calculation of this study is therefore based on the primary endpoint for itch assessment. An open-label internal Pfizer study with a similar scale to the Observer Reported Itch Assessment in 3-months to 5-year olds, the reduction of itch/scratch was evaluated from baseline to 14 days. Based on the results of that study, a 2.6 points common standard deviation in the observer reported pruritus score change from baseline for 2 weeks in children ages 3 months to 5 years with mild to moderate AD was assumed. There is no data available for 6 \leq 11 year olds. Therefore, the assumption is made that children ages 6 to \leq 11 will have the same standard deviation. We will employ a simple randomized procedure using a computerized random numbers to assign participants to the two groups. A total of 244 randomized participants (in 1:1 ratio) will provide approximately 85% power to detect a 1.0 points of the observer reported pruritus score reduction difference in crisaborole treatment group compared to vehicle group, with a two-sided 5% significance.

With an expected dropout rate of ~10%, approximately 540 (270 children and 270 primary adult caregivers) are expected to be recruited for this study.

Statistical Methods and Analysis:

The primary and secondary endpoints will be tested at the significance level of 0.05 (2-sided). There is no multiplicity adjustment. Number, percent and 95% confidence interval (CI) will be presented for binary endpoints. Descriptive summary statistics (n, Mean, Std. Dev, Median, Min., Max.) will be presented for continuous endpoints. In addition, graphics may be used to present the data.

The primary objective is to evaluate the effects of Crisaborole on itch and night-time scratch. The primary endpoints include number of scratching episodes (children aged 2 – \leq 11 years), duration of scratching (children aged 2 – \leq 11 years), and ORIA (ages 3 months to \leq 11 years). For these endpoints, change from baseline will be analyzed using a mixed-effects model with repeated measures (MMRM) including data from Day 1 (for accelerometry measured scratch episodes and duration)/Day 2 (for ORIA) to Day 15 with baseline score as a covariate and an unstructured covariance matrix. The least-squares (LS) means and

the corresponding 95% CIs, the LS mean difference between treatment groups, and the corresponding 95% CI will be presented for change from baseline for all postbaseline timepoints. As a sensitivity analysis, instead of daily data, average of every 3 days data will be used to account for day-to-day variation.

The binary endpoints will be descriptively summarized using sample size, number, percentage and 95% confidence interval (CI) of percentage at each time point. Binary data will be analyzed by comparing response rates between treatment groups. Normal approximation to the difference in response rates will be used to obtain p-values and 95% CI. For binary endpoints analyzed at each scheduled visit separately, participants who drop out for any reason or require a prohibited medication for the treatment of their atopic dermatitis will be defined as “non-responsive” at all subsequent visits. This method of handling missing response is known as missing response as non-response (MR-NR).

Mixed model repeated measures (MMRM) will be used to analyze longitudinal continuous data. Treatment, visit, treatment-by-visit interaction are fixed effects in the model, baseline value as a covariate. Within-participant variability will be accounted for using a random effect with the unstructured covariance matrix. If this is a convergence issue, other type of covariance matrix will be used. The following structures will be executed in the order specified (essentially in decreasing order of complexity) until convergence is achieved: heterogeneous Toeplitz, heterogeneous first order autoregressive, autoregressive, heterogeneous compound symmetry, compound symmetry, and variance components. The first structure yielding convergence will be used as the primary analysis. The Kenward and Roger method for calculating the denominator degrees of freedom for tests of fixed effects will be used. Least square (LS) estimates of mean values and the LS mean differences between crisaborole 2% BID and vehicle groups at each visit will be derived from the model. The corresponding p-value, standard error (SE) and 95% CI will also be derived from the model.

ANCOVA model will be used to analyze nonlongitudinal continuous endpoints with treatment as a factor baseline value as a covariate. Least square (LS) estimates of mean values and the LS mean differences between crisaborole 2% BID and vehicle groups at each visit will be derived from the model. The corresponding p-value, standard error (SE) and 95% CI will also be derived from the model.

For any accelerometry/actigraphy continuous variables that exhibit right skewed distribution (i.e. skewed to positive values), log transformation may be used as appropriate. Specifically, for number of scratching, length of time scratching, arousals from sleep, WASO, and sleep onset latency, $\log(x+1)$ transformation will be employed (to include possible zero values). For time duration between scratching, $\log(x)$ will be employed.

For efficacy continuous endpoint not measured longitudinally, the post-baseline missing values will not be imputed, ie, the values are assumed to be missing completely at random. For efficacy continuous endpoints measured longitudinally, missing values post-baseline will be handled in a linear mixed-effect model with repeated measures for this continuous variable, where the values are assumed to be missing at random. For the continuous ObsROs variables, rules suggested by the developers of these instruments will be followed in calculating the missing values. If these rules are not enough for imputing a value, then the missing values will be handled in the same way as efficacy variables.

Specific analyses to be conducted:

- Evaluate drug-induced changes of itch ORIA, scratching and sleep quantity, and additional PRO/ObsRO and biomarkers; comparing start of the study to measures obtained while on treatment
- Summary of AEs and RRIs

- Comparison of PRO/ObsRO assessments to scratching and sleep values obtained from device measurements.
- Comparison of digital measures of scratching and sleep with QoL PRO assessments.

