Appendix B: PATIENT REPORTED OUTCOME (PRO) / OBSERVER REPORTED OUTCOME(ObsRO) ASSESSMENTS

Observer Reported Itch Assessment

The Observer Reported Itch Assessment assesses the severity of itch (pruritus) in the child due to AD. The participants primary caregiver will be asked to assess their child's worst itch (i.e., scratching, rubbing) due to AD over the past 24 hours in an eDiary every day during the study. Observer Reported Itch Assessment for 3 months - ≤ 11 years of age is an 11-point scale and must be completed by an observer (caregiver). Instruments to be provided to participants as age appropriate below:

Subject ID: _____

Date: _____

Observer Reported Itch Assessment for ages ≥3 months to <2 years of age:

On a scale of 0 to 10, with 0 being "no itch" and 10 being "worst itch imaginable", how would you rate your observation of your child's itch (i.e., scratching, rubbing) at the worst moment during the previous 24 hours?

Cannot answer. I am unable to observe signs of itch-related

|

Subject ID: _____

Date: _____

Observer Reported Itch Assessment for ages ≥ 2 years to ≤ 11 of age:

On a scale of 0 to 10, with 0 being "no itch" and 10 being "worst itch imaginable", how would you rate your observation of your child's itch (i.e., scratching, rubbing) at the worst moment during the previous 24 hours?

Subject ID: _____

Date: _____

Technician Initials: _____

PAD Patient Reported Itch Severity Scale for 6-11 years of age:

Select the face that shows how itchy your skin has been today:

Not Itchy

Very Itchy

Subject ID: _____

Date: _____

Observer Reported Global Impression Severity (OGIS)

The scale will be completed by an observer every day, preferably at the same time as the Observer Reported scratch assessment. The Observer Reported Global Impression Severity (OGIS) is a one-item 7-point rating scale and completed by observers/caregivers of subjects to assess a subject's illness severity at a given point in time. The OGIS will be used as an anchor for defining a "clinical important difference" on the scratch assessments and can also be used to create severity categorization to enhance interpretation. The observer/caregiver of a child is asked to rate the severity of an illness of the child right now as follows:

Please rate the severity of the child's atopic dermatitis right now (select only ONE response):

Not present	
Very mild	
Mild	

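### The MMRM adjusts only for the endpoint's own baseline value; pre-specifying baseline-by-visit, age group and baseline EASI would be a nearly free improvement, though their absence is not an error

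*Combined protocol and SAP*

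**What the plan says.** Section 9, Statistical Methods and Analysis, applies an MMRM on change from baseline to the three primary endpoints: number of scratching episodes and duration of scratching (both ages 2 to 11 years), and ORIA (3 months to 11 years). The baseline score is the only covariate and the covariance is unstructured. The general description for longitudinal continuous data is the same: "Treatment, visit, treatment-by-visit interaction are fixed effects in the model, baseline value as a covariate". The ANCOVA for non-longitudinal endpoints has treatment and the baseline value. Neither model contains a baseline-by-visit term, age, ISGA, EASI or %BSA.

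On allocation, Section 3 states that "we will employ a simple randomization procedure", at 1:1 and with no stratification factor. Age and eligibility are established at V01, and ISGA, EASI and %BSA are scored there (Schedule of Activities; Section 5).

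The sample size rests on "a 2.6 points common standard deviation in the observer reported pruritus score change from baseline for 2 weeks". Section 9 then states: "A total of 244 randomized participants (in 1:1 ratio) will provide approximately 85% power". The treatment effect behind that figure is 1.0 point on the ORIA-type score, and the test is specified "with a two-sided 5% significance". No reduction in SD is taken for any covariate.

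**The concern.** Three features of this trial make the short covariate list worth a second look.

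- **Age.** The children run from 3 months to 11 years, with about half intended to be 5 or younger. Under Section 4.1, an ORIA score of at least 2 is required only up to age 5. Ages 6 to 11 qualify on a child-reported scale, so baseline ORIA may be distributed differently in the two groups. The SD for ages 6 to 11 is assumed, because Section 9 has no data for them.
- **Severity.** Section 8.2 withdraws children whose BSA passes 40% at visits 3 and 4, and the MMRM assumes missing at random. Baseline severity in the model would make that assumption more credible.
- **Daily estimates.** The plan reports a treatment difference at every post-baseline time point, and rapid onset is a stated aim. A single baseline slope has to serve both the first and the last day.

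At stake are the width of the daily confidence intervals and how far a chance difference between arms in age or severity carries into the estimated effect.

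**Working it through.** **1. The plan's own figure.** Inputs from Section 9: difference 1.0, SD 2.6, two-sided 5%, 1:1.

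- Required n per arm for 85% power: 2 × (1.960 + 1.036)² × 2.6² / 1.0² = 121.4, so 122 per arm and 244 in total. This matches the plan.
- Power at 122 per arm: noncentrality 1.0 / (2.6 × √(2/122)) = 3.004. This gives 84.9% by noncentral t (242 df), or 85.2% by the normal approximation.

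The 2.6 is the SD of the change score itself, so the stated power does not draw on any covariate.

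**2. Age group and baseline severity.** If these explain a further share R² of the variance, the SD becomes 2.6 × √(1 − R²) and the equivalent sample size is 244 / (1 − R²). The documents give no R²; the values below are assumptions.

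| Assumed R² | SD | Power (noncentral t) | Equivalent N | Gain in children |
|---|---|---|---|---|
| 0 | 2.600 | 84.9% | 244 | 0 |
| 0.02 | 2.574 | 85.6% | 249 | 5 |
| 0.05 | 2.534 | 86.6% | 257 | 13 |
| 0.10 | 2.467 | 88.4% | 271 | 27 |

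**3. Chance imbalance in age.** With half the children aged 5 or younger and 122 per arm, the standard error of the between-arm difference in that share is √(2 × 0.25 / 122) = 0.064. A difference of 10 percentage points or more is 0.10 / 0.064 = 1.56 standard errors, with probability about 12%.

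**4. One slope for all days.** Standardise the baseline and each daily score to variance 1, and let ρ_t be their correlation on day t. A day-specific slope leaves residual variance 1 − ρ_t². A common slope b leaves 1 − ρ_t² + (ρ_t − b)², so the proportional excess is (ρ_t − b)² / (1 − ρ_t²). Analysing change scores shifts every slope by −1 and leaves this excess unchanged.

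The MMRM estimates b by generalised least squares, b = (1′S⁻¹ρ) / (1′S⁻¹1), where S is the residual covariance. Assume 14 days, linear drift in ρ_t and first-order autoregressive residuals with autocorrelation 0.6 to 0.9:

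- Mild drift, 0.6 to 0.4: excess about 1-2% on the first and last days. For example, at autocorrelation 0.6, b = 0.507; the last day gives (0.4 − 0.507)² / (1 − 0.16) = 1.4%.
- Strong drift, from 0.7-0.8 down to 0.3-0.4: about 2-10% on the first day and 3-16% on the last. For example, for 0.8 to 0.3 at autocorrelation 0.9, b = 0.685; the last day gives (0.3 − 0.685)² / (1 − 0.09) = 16%.

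The strong-drift result is sensitive to the residual correlation. Mixing compound symmetry with the autoregressive form gave a last-day excess up to about 24% in most settings, and more in some.

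**5. Simulation check.** This used 244 children, 14 visits, complete data and last-visit change SD fixed at 2.6, with baseline SD assumed at 1.5 or 2.0. The last-visit variance under a common slope, relative to visit-specific slopes, was 0.99 to 1.01 when the change-score slope moved from −0.3 to −0.5. It was 1.02 to 1.03 for −0.2 to −0.6, and 1.03 to 1.09 for −0.1 to −0.7. The treatment estimate showed no material bias.

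**The case against.** The strongest reply is that nothing here is wrong. Randomisation is unstratified, so no stratification factor has been dropped from the model. The randomised comparison is valid without further covariates, and its standard error already allows for chance imbalance. The sample size is met without them. ISGA is restricted to 2 or 3 at entry and baseline itch is already adjusted for, so the added R² could be close to zero. All of this stands, and it is why the point is an improvement only.

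Two stronger readings are tempting. A reader might infer that the trial loses precision it had planned on; the sample size calculation shows otherwise, since no covariate gain was assumed. A reader might also infer from "Instruments to be provided to participants as age appropriate below" that ORIA scores differ in kind below and above 2 years. The two forms show the same question, 24-hour recall and 0 to 10 range. The visible difference is an option, on the younger form only, for a caregiver who cannot answer, so the forms alone do not establish an instrument effect.

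Three practical objections also have force:

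- An age category below 2 years would be empty for the two scratch endpoints.
- Baseline EASI would duplicate the existing covariate where EASI is the outcome.
- Age and EASI as main effects carry one coefficient across all days, the same restriction questioned for baseline. That is a fair trade for a smaller model.

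The fix below deals with the first two and accepts the third.

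**Conclusion.** The point holds as an optional, low-cost improvement. The model leaves out age, baseline severity and a baseline-by-visit term although the data are in hand and the allocation does not balance them. The planned analysis is valid, and its stated power of about 85% is reproduced without these terms.

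The gain cannot be fixed from the documents, which give neither an R² nor a baseline-outcome correlation. Under assumed R² of 0.02 to 0.10, power rises by 0.7 to 3.5 percentage points; at R² near zero it does not move. The common slope costs little under mild drift and matters mainly on late days under strong drift, with a size that depends on the unknown residual correlation. The omission should not be described as a source of bias: with complete data none appeared in the simulation.

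**What to change.** Amend the SAP text in Section 9 before unblinding, so that the added terms cannot be seen as post hoc:

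- **MMRM:** add baseline-by-visit interaction, age group at V01 and baseline EASI as fixed effects. Use age groups <2, 2-5 and 6-11 years for ORIA, and 2-5 and 6-11 years for number and duration of scratching. Omit the additional EASI term where EASI is itself the outcome.
- **ANCOVA:** add age group and baseline EASI, with the same exception.
- EASI is preferable to ISGA as the severity term, because entry criteria leave ISGA only two levels.

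No new data are needed. Baseline-by-visit adds 13 to 14 parameters for 14 to 15 time points. Age and EASI add 3 for ORIA (two for age, one for EASI) and 2 for the scratch endpoints. The unstructured covariance already needs 14 × 15 / 2 = 105 to 15 × 16 / 2 = 120 parameters, so convergence is a real consideration. The fallback sequence of covariance structures already in Section 9 continues to cover it.
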